#### 4.4. Populations for the Open Label Extended Treatment Phase

Population	Definition / Criteria	Analyses Evaluated
Intent-To-Treat-Exposed OL_ETP (ITTE OL_ETP)	
 
• All participants who received at least one dose of study treatment in the OL ETP
 
• This population will be based on the treatment that the participant was allocated to.
 
	
 
• Study Population
 
• Efficacy
 
• PD
 
• Biomarker
 
• PRO
 

Safety OL_ETP	
 
• All participants who received at least one dose of study treatment in the OL_ETP.
 
• This population will be based on the treatment the participant actually received.
 
	
 
• Safety
 

Pharmacokinetic ETP (PK_Ol_ETP)	
 
• All participants in the Safety OL_ETP population who had at least 1 non-missing PK assessment in OL ETP (Non-quantifiable [NQ] values will be considered as non-missing values).
 
	
 
• PK
 

Refer to Section [15.5.2](#): Reporting Standards for rules used to define ‘treatment actually received’.

Refer to [Appendix 12](#): List of Data Displays which details the population used for each display.

## 4.5. Protocol Deviations

Important protocol deviations (including deviations related to study inclusion/exclusion criteria, conduct of the trial, patient management or patient assessment) will be summarised and listed.

Protocol deviations may define Intercurrent Events (ICEs) that affect Efficacy analyses, as described in Section [8.1.1.1](#) and Section [8.2.1.1](#). ICEs will be listed as described in [Appendix 12](#): List of Data Displays.

Protocol deviations will be tracked by Robarts and monitored by the GSK study team throughout the conduct of the study in accordance with the Protocol Deviation Management Plan which will be updated throughout the study

- The protocol deviations for those participants included in each interim analysis, up to the point of the data cut-off will be reviewed prior to unblinding.
- Data will be reviewed prior to unblinding and freezing the database to ensure all important deviations and deviations which may lead to exclusion from the analysis are captured and categorised consistently on the protocol deviations datasets.
- This dataset will be the basis for the summaries and listings of protocol deviations.

A separate summary and listing of all inclusion/exclusion criteria deviations will also be provided. This summary will be based on data as recorded on the inclusion/exclusion page of the eCRF.

## 5. CONSIDERATIONS FOR DATA ANALYSES AND DATA HANDLING CONVENTIONS

### 5.1. Study Treatment & Sub-group Display Descriptors

#### 5.1.1. Randomised, Double Blind Treatments

For within-study phase reporting the following descriptions will be used.

Treatment Group Descriptions			
RandAll NG Randomization System		Data Displays for Reporting where characters are limited	
Code	Description	Description	Order in TLF
A	GSK2831781 450 mg IV	GSK2831781 450 mg IV	2
B	GSK2831781 300 mg IV	GSK2831781 300 mg IV	3
C	GSK2831781 150 mg IV	GSK2831781 150 mg IV	4
D	GSK2831781 45 mg IV	GSK2831781 45 mg IV	5

Treatment Group Descriptions			
RandAll NG Randomization System		Data Displays for Reporting where characters are limited	
Code	Description	Description	Order in TLF
P	Placebo IV	Placebo IV	1
X	GSK2831781 300mg SC	GSK2831781 300mg SC	7
Y	Placebo SC	Placebo SC	6

Treatment comparisons in induction will be displayed as follows using the descriptors as specified:

1. GSK2831781 450 mg IV vs Placebo IV
2. GSK2831781 300 mg IV vs Placebo IV
3. GSK2831781 150 mg IV vs Placebo IV
4. GSK2831781 45 mg IV vs Placebo IV
- 5.
6. For reporting **within** the extended treatment phase the following treatment descriptions will be used.

7. Treatment Group Descriptions – Extended Treatment Phase for week 10 responders			
RandALL NG Randomization System		Data Displays for Reporting where characters are limited	
Code	Description	Description	Order in TLF
8. AX	9. GSK2831781 450 mg IV induction, 300 mg subcutaneous from week 14	10. 11. 12. 13. 14. GSK2831781 300mg SC	15. 2    18. 2   21. 2  24. 2
16. BX	17. GSK2831781 300 mg IV induction, 300 mg subcutaneous from week 14		
19. CX	20. GSK2831781 150 mg IV induction, 300 mg subcutaneous from week 14		
22. DX	23. GSK2831781 45 mg IV induction, 300 mg subcutaneous from week 14		
25. PY	26. Placebo IV induction, Placebo subcutaneous from week 14	27. Placebo SC	28. 1

Treatment comparisons in the extended treatment phase will be displayed as follows using the following descriptor as specified:

GSK2831781 300 mg SC vs Placebo SC

### 5.1.2. Partial doses

If an incomplete IV dose is given then the dose received will be calculated as a proportion of the planned dosing duration (see below), this makes the simplifying assumption that the IP will be dosed at a constant rate. If an incomplete SC dose is given, the number of injections will be used to derive the received dose. For details of these calculations see Section [15.6 Appendix 6: Derived and Transformed Data](#).

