6.2. Intervention Administration

GSK2831781 is a fully humanized monoclonal antibody and all formulation ingredients have been previously used in the clinic. The intervention administration timings and monitoring periods as shown in [Table 1](#) (Responders) and [Table 2](#) (Open Label) must be undertaken for each participant.

Table 1 Intervention Duration and Monitoring Schedule (Double-Blind Induction and Double-Blind Extended Treatment Phase)

Dose	Dosing Duration*	Monitoring period
IV (Week 0, Day 1)	2 hr	2 hr
IV (Week 2)	2 hr	2 hr
IV (Week 6)	32 min	1 hr
IV (Week 10)	32 min	30 min
SC (Week 14)	n/a	2 hr
SC (Week 18)	n/a	30 min
SC (Week 22)	n/a	n/a
SC (Week 26)	n/a	n/a

* Including flush, see Study Reference Manual for details.

Table 2 Intervention Duration and Monitoring Schedule (Open Label Induction and Open Label Extended Treatment Phase)

Dose	Dosing Duration*	Monitoring period
IV (Week 12)	2 hr	2 hr
IV (Week 14)	2 hr	2 hr
IV (Week 18)	32 min	1 hr
IV (Week 22)	32 min	30 min
SC (Week 26)	n/a	2 hr
SC (Week 30)	n/a	30 min
SC (Week 34)	n/a	n/a
SC (Week 38)	n/a	n/a

* Including flush, see Study Reference Manual for details.

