8.6.5. Immunogenicity Assessments

Antibodies to GSK2831781 will be evaluated in serum samples collected from all participants according to Section 1.3. Additionally, serum samples will also be collected at the Withdrawal visit from participants who discontinued study intervention or were withdrawn from the study. The detection and characterization of antibodies to GSK2831781 will be performed using a validated assay method by or under the supervision of the Sponsor.

Serum samples will be assessed for the presence of ADA using a tiered approach. Samples will first be screened for antibodies binding to GSK2831781. Samples with screening result above the screening cut point will be further assayed in an assay to confirm the specificity of the ADA. Samples testing positive in the confirmation assay will be further assayed through sequential dilution in order to report a titre value. The titre is the reciprocal of the last dilution at which the sample tests positive in the screening assay. Additional analysis may be performed on samples collected to monitor immunogenicity to assess the

presence of neutralizing antibodies to GSK2831781 and/or to further characterize the immunogenicity of GSK2831781.

8.6.6. Infusion-related Reactions, Hypersensitivity Reactions and Cytokine Release Syndrome.

As GSK2831781 is a fully humanized monoclonal antibody, it is considered unlikely that acute allergic reactions will occur in response to GSK2831781 exposure; however, all participants should be monitored carefully for evidence of allergic response. In the event of a suspected acute hypersensitivity reaction two blood samples should be taken for serum tryptase analysis:

- As soon as possible after the onset of symptoms, and
- Within 1-2 hours (but no later than 4 hours) from the onset of symptoms.

Participants should be instructed to report the development of rash, hives, pruritus, flushing, urticaria, vomiting, or other symptoms that may represent a hypersensitivity reaction to study intervention. In the case of a mild reaction, study intervention administration may be reinitiated (with appropriate pre-medication) at the discretion of the Investigator. Participants with a serious or severe clinically significant hypersensitivity reaction following study investigational product administration meeting the CTCAE criteria set out in Section 7.1.1 should discontinue study treatment.

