## Overview of Study Design and Key Features

## Extended Treatment Phase – Dosing regimen for Responders only

## Open Label Treatment – Dosing Regimen for Non-Responders

## Week 10 Non-Responders

- Participants identified as Non-Responders at Week 10 will be assigned to open label treatment in the Open Label Induction Phase. The total duration of open label treatment will be up to an additional 30 weeks of treatment (Week 12 to Week 42) and a 12-week Follow-Up. Participants who have not attained clinical response, determined following a centrally read endoscopy at Week 22 (calculated centrally through the eCRF), will discontinue study treatment and are still required to attend a Follow-Up visit approximately 16 weeks from the last dose event.
- Participants in the Open Label part who respond at Week 22 will then receive 300mg GSK2831781 subcutaneously (SC) every four weeks during the Open Label Extended Treatment Phase (ETP), from Week 26 until Week 38.
- Subsequently, all Open Label participants will remain in study, but off treatment, to Week 54 in the 12-week Open Label Follow-Up phase.

[figure not shown]
Overview of Study Design and Key Features	
Dosing	
INDUCTION Phase:
 
 
• GSK2831781 450 mg IV
 
• GSK2831781 300 mg IV
 
• GSK2831781 150mg IV
 
• GSK2831781 45mg IV
 
• Placebo IV
 
 
EXTENDED Treatment Phase for RESPONDERS
 
 
• GSK2831781 300 mg SC
 
• Placebo SC
 
 
OPEN LABEL Treatment Phase for NON-RESPONDERS
 
 
• GSK2831781 450 mg IV – weeks 12, 14, 18 and 22
 
• GSK2831781 300 mg SC for Open Label Responders (assessed at week 22)
 
• Treatment discontinuation for Open Label Non-Responders (assessed at week 22)
 

Time & Events	
 
• Refer to Appendix 2: Schedule of Activities (SoA)
 

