### 15.6.2. Study Population

Exposure
Partial Doses

 
For partial IV doses, the quantity of IP given to the participant will be calculated using the simplifying assumption that IP is dosed at a constant rate using the following formula:  IP dose received = IP dose expected * ((dose stop time – dose start time) / expected duration of dosing) 
 
Section 5.1.2 shows the expected duration of dosing which is dependent on visit.
 
For partial SC doses, the quantity of IP given to the participant will be calculated based on the number of injections received. The expected SC dose is always two injections (2 x 150mg) so a single injection will dose 150mg.
 

Number of Doses
Summarise the number of doses received by participants within each study phase.
Cumulative Dose
The cumulative received dose in mg will be calculated across all phases and within each study phase for each participant.
Duration of Exposure

The number of days of exposure will be calculated for each participant within study phase and across all study phases.
 
 
The following algorithm will be used for calculating days exposed across all study phases:
 
 $\text{Duration of Exposure} = \text{Last dose date} - \text{first dose date} + 1$

2. The following algorithm will be used for calculating days exposed in a study phase:

$$\text{Duration of Exposure} = \text{Last dose date of phase} - \text{first dose date of phase} + 1$$

Note: subjects with multiple missed doses in a phase are not expected to start the next phase.

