1.36.	ITTE	Take elements from EX1 and EX5	Summary of Exposure to Study Treatment in Induction Phase	ICH E3 Length of exposure (days) within study phase and in the study Cumulative dose (mg) [in shell EX1] report cumulative dose only for current study phase Summarise number of doses received as categorical [replaces cycles, shell EX5] (use levels 1, 2, 3, 4 doses). Footnotes: “Dose” is planned dosing events, not number of injections, and includes partial doses.”	SAC

Study Population Tables					
No.	Population	IDSL / Example Shell	Title	Programming Notes	Deliverable [Priority]
1.37.	ITTE_ETP	EX1 and EX5	Summary of Exposure to Study Treatment in Extended Treatment Phase	
ICH E3
 
Items as for induction phase, except for length of exposure in the study.
 
Footnote:
 
“Exposure is summarised within the current study phase except where specified.
 
“Dose” is planned dosing events, not number of injections, and includes partial doses.”
	SAC
1.38.	ITTE_OL_I	EX1 and EX5	Summary of Exposure to Study Treatment in Open Label Induction Phase	
ICH E3
 
Items as for induction phase, except for length of exposure in the study.
 
Footnote:
 
“Exposure is summarised within the current study phase.
 
“Dose” is planned dosing events, not number of injections, and includes partial doses.”
	SAC

Study Population Tables					
No.	Population	IDSL / Example Shell	Title	Programming Notes	Deliverable [Priority]
1.39.	ITTE_OL_ETP	EX1 and EX5	Summary of Exposure to Study Treatment in Open Label Extended Treatment Phase	ICH E3 Items as for induction phase, except for length of exposure in the study.  Footnote: "Exposure is summarised within the current study phase. "Dose" is planned dosing events, not number of injections, and includes partial doses."	SAC

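### The SAP's clock-time rule for an incomplete IV dose counts paused minutes as drug given and has no upper limit, so an infusion resumed and then abandoned can be credited with more than its planned dose

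*SAP*

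**What the plan says.** SAP 5.1.2 sets the principle for a partly given infusion: "If an incomplete IV dose is given then the dose received will be calculated as a proportion of the planned dosing duration". It adds that "this makes the simplifying assumption that the IP will be dosed at a constant rate", and sends the reader to Appendix 6 for the calculation. There, SAP 15.6.2 gives the operative formula: "IP dose received = IP dose expected * ((dose stop time – dose start time) / expected duration of dosing" (closing bracket omitted here). On the denominator it says: "Section 5.1.2 shows the expected duration of dosing which is dependent on visit". The table in 5.1.2 lists 2 hours for Day 1 and Weeks 2, 12 and 14, and 32 minutes for Weeks 6, 10, 18 and 22.

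Neither section deducts time when the infusion was not running, limits the result to the expected dose, or defines start and stop for an interrupted infusion. Partial SC doses are handled differently, by counting injections.

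The derived dose feeds cumulative dose in milligrams. SAP 15.12.4 plans this for Table 1.36 with the note "report cumulative dose only for current study phase", and Tables 1.37 to 1.39 carry the same items for the other phases. All four are final-analysis outputs on the intent-to-treat-exposed populations.

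**The concern.** The formula is used only for incomplete infusions, and some of those will have been interrupted. Interruption is foreseeable. Protocol 8.6.6 says: "In the case of a mild reaction, study intervention administration may be reinitiated (with appropriate pre-medication) at the discretion of the Investigator". When an infusion is paused, restarted and then given up, every paused minute is counted as drug delivered. A rate that was slowed and never restored has a similar effect, because elapsed time is converted to milligrams at the planned rate.

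At stake is a descriptive result. A participant who received well under the planned dose can appear in the exposure summary as having received all of it or more. More than 100% from an infusion already classed as incomplete cannot be right, and it hides the under-dosing that the rule was written to capture.

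**Working it through.** **Inputs.** The expected dose D is 450 mg (SAP 2.3, "GSK2831781 450 mg IV"); percentages are the same at 300, 150 and 45 mg. The planned duration T is 120 or 32 minutes (SAP 5.1.2). Minutes infused (I) and minutes paused (P) are assumptions, since the documents give neither. The plan states no figure of its own on this point, so there is nothing to reproduce.

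**Formulas.** Take start as the initial start and stop as the final stop.
- Credited by SAP 15.6.2: D × (I + P)/T
- Given at the planned constant rate: D × I/T
- Excess: D × P/T
- Credit exceeds D when I + P > T, that is, when P > T − I.

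**Main example.** A 120-minute infusion runs 30 minutes, is paused for 60, runs 45 more and is stopped for good. So I = 75 and P = 60.
- Credited: 450 × 135/120 = 506.25 mg (112.5%)
- At the planned rate: 450 × 75/120 = 281.25 mg (62.5%)
- Excess: 450 × 60/120 = 225 mg
- The credit reaches 100% at a pause of 120 − 75 = 45 minutes.

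**Range, with 75% of the planned time infused (337.5 mg at the planned rate).**

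| T (min) | I (min) | P (min) | Credited (mg) | % of planned |
|---|---|---|---|---|
| 120 | 90 | 0 | 337.5 | 75 |
| 120 | 90 | 30 | 450 | 100 |
| 120 | 90 | 60 | 562.5 | 125 |
| 32 | 24 | 8 | 450 | 100 |
| 32 | 24 | 20 | 618.75 | 137.5 |
| 32 | 24 | 30 | 759.4 | 168.8 |

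With 50%, 75% and 90% of the planned time infused, the pause that brings the credit to 100% is 60, 30 and 12 minutes for a 2-hour infusion, and 16, 8 and 3.2 minutes for a 32-minute one. The short infusions are the more sensitive.

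**What each remedy does to the main example.** Deducting the pause returns 281.25 mg. A cap alone returns 450 mg, still 450 − 281.25 = 168.75 mg too high.

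**Effect of the flush.** Protocol 6.2 notes on the planned durations: "Including flush, see Study Reference Manual for details". Dividing by the whole of T therefore understates drug given before the flush. The flush length is not given. Assuming 2 minutes within a 32-minute infusion, 24 minutes of drug is 24/30 = 80%. With a 1-minute pause the SAP formula gives 25/32 = 78%, slightly too low. Under that assumption the pause must exceed 24 × 2/30 = 1.6 minutes before the dose is overstated.

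**Which tables.** Table 1.36 (double-blind induction) and Table 1.38 (open-label induction) cover IV dosing. Tables 1.37 and 1.39 cover the extended treatment phases, where dosing is SC and only current-phase dose is reported, so no IV dose enters them.

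**Populations.** SAP 4.1 defines the induction ITTE population by randomised treatment and requires at least one valid post-dose assessment. The Safety population requires only a dose and is grouped by treatment actually received. A participant who reacts to the opening infusion and leaves without a valid assessment would be in the adverse event tables but not in Table 1.36. In the later phases (SAP 4.2 to 4.4) both populations require only a dose in that phase, so they differ in treatment grouping, not in who is included.

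**The case against.** The strongest reply is that the trigger is narrow. An infusion stopped once and not resumed contains no pause, and the formula then works as intended. One that is paused, resumed and completed is not incomplete, so the rule does not apply. The error needs a pause, a resumption and a permanent stop within one infusion, or a slowed rate. Protocol 8.6.6 does not say that the same infusion is resumed; it can equally be read as allowing later dosing. Protocol 2.3.1 reports no infusion reactions in the Phase 1 studies. If the eCRF records each infusion segment, summing segments removes the problem, and the SAP openly calls its rule a simplification.

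All of that stands, and it keeps the point small. It does not remove it: the written formula has no pause term or limit, and the SAP does not say that segments are summed.

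Three stronger readings are tempting, and the documents do not support them. A reader might infer that all four exposure tables misstate dose, but two of them contain only SC dosing. A reader might infer that a pause always leads to overstatement, but because planned duration includes the flush, a short pause may leave the figure too low. A reader might infer that efficacy or safety comparisons are distorted. However, the models in SAP 8.1.1.2 and 8.2.1.2 use treatment arm, the adverse event tables are by treatment and phase, and exposure-adjusted rates (SAP 15.6.4) use days. The PopPK and PK/PD dataset specifications are separate documents, so their use of this figure cannot be judged.

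On the population change, blinded Table 1.35 is weak precedent. It uses the Safety population but shows nothing by treatment.

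**Conclusion.** The point holds as a minor defect in a stated derivation. As written, SAP 15.6.2 credits paused minutes as dose. It gives more than 100% of the planned dose whenever the pause exceeds the planned time left uninfused: 506 mg against 281 mg in the main example. This rests on three assumptions: the recorded times are the initial start and final stop, the infusion was paused, resumed and then abandoned, and drug ran at the planned rate while the infusion was on. The pause lengths are illustrative. The number of such infusions is not given and is probably small. The effect is confined to cumulative dose in Tables 1.36 and 1.38.

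The population point stands separately and covers Tables 1.36 to 1.39. For milligrams actually given, grouping by treatment received is the natural choice, and in induction it also aligns the participants with those in the adverse event tables.

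**What to change.** In SAP 5.1.2 and 15.6.2:
1. Where infused volume was recorded, derive the dose from it. This also deals with a slowed rate and the flush, which a time-based rule cannot.
2. Otherwise use expected dose × min(1, total actual infusion time excluding interruptions / planned duration), and state how start and stop are taken when an infusion has more than one segment.
3. Where neither volume nor interruption time is recorded, apply the cap and flag the dose as incomplete with amount uncertain. The cap removes impossible values but does not correct the overstatement, so the figure should not pass as a measured dose.

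Separately, in SAP 15.12.4, move Tables 1.36 to 1.39 to the corresponding Safety populations.

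The cost is one revised formula, one flag and four population labels, with the matching programming. No dose, schedule or efficacy analysis changes. Whether steps 1 and 2 can be applied depends on what the infusion record holds, which the documents do not show.

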#### Planned dose duration for IV doses

Phase	Visit	Planned duration of IV dose
Induction	Day 1	2 hr
Induction	Week 2	2 hr
Induction	Week 6	32 min
Induction	Week 10	32 min
Open label induction	Week 12	2 hr
Open label induction	Week 14	2 hr
Open label induction	Week 18	32 min
Open label induction	Week 22	32 min
See protocol Table 1 and Table 2 for further context		

### 5.2. Baseline Definitions

The baseline value will be the latest pre-dose assessment with a non-missing value, including those from screening and unscheduled visits

If baseline data is missing no derivation will be performed and baseline will be set to missing.

### 5.3. Multicentre Studies

In this multicentre global study, enrolment will be presented by the investigative site. Participants will be enrolled from approximately 100 centres. There are no planned adjustments made for multiple centres in this study.

## 5.4. Examination of Covariates, Other Strata and Subgroups

### 5.4.1. Covariates and Other Strata

The following list of covariates and other strata will be used in descriptive summaries and statistical analyses of primary and key secondary efficacy endpoints, some of which will also be used for subgroup analyses. Additional covariates and other strata of clinical interest may also be considered. For change from baseline endpoints, the baseline will also be included as a covariate.

Category	Details	Notes
Advanced therapy experience (Stratification factor)	Categorical variable with three levels: 
 
Advanced therapy naïve,
 
Single class of advanced therapy experience
 
Multiple classes of advanced therapy experience
 
	Derived from 'previous UC medications' in medical history.  This is the stratification factor used in RAMOS, recorded at baseline in the eCRF for each participant; in case of conflict between the stratification in RAMOS and medical history, medical history will be used.
TNF failure (Covariate)	Categorical variable with three levels: 
 
No TNF failure
 
Single TNF failure
 
Multiple TNF failures
 
	Derived from medical history, covariate will be used as secondary analysis at primary completion
biologic experience type (Covariate)	Categorical variable with three levels: 
 
Biologic naïve
 
TNF experience (no Vedolizumab)
 
Vedolizumab (including participants who have both TNF and Vedolizumab experience)
 
 
Note: if participant has experience of other biologics, they will be assigned based on experience of TNF and Vedolizumab.
	Derived from medical history. Comparison made as secondary analysis.
Baseline mucosal CD3+LAG3+ cell count (Covariate)	Continuous variable derived from biopsy.  CD3 positive and Lag3 positive cells per mm  of Lamina Propria tissue taken at screening biopsy.	
Duration of disease (Covariate)	Duration of disease, years	If day and month of diagnosis are missing, duration of disease will be calculated by using day=1 and month=July
Baseline Complete Mayo Score	Where the endpoint is derived from a version of the Mayo score, that version's baseline will be used.	

Category	Details	Notes
Baseline Adapted Mayo Score	Where the endpoint is derived from a version of the Mayo score, that version's baseline will be used.	

